## 2.0 OBJECTIVE

The primary objective of this protocol is to investigate if pre-operative inter-papillary muscle separation (IPMS) is predictive of FMR severity at 12 months after undersizing mitral annuloplasty (UMA) to repair functional mitral regurgitation (FMR). Furthermore, whether a cut-off value of pre-operative inter-papillary muscle separation can be established to predict patients who might have failure of UMA.

The secondary objective of this protocol is to investigate if adding papillary muscle approximation (PMA) to UMA is an effective technique in reducing recurrence of FMR at 12 months' post-procedure.

The third objective is to use computational modeling to define the impact that IPMS has on chordal force imbalance, to define the mechanistic basis for repair failure. MRI and echo images from the patients will be used to accomplish this objective.

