## 9.0 DEFINITIONS AND MEASUREMENT OF ENDPOINTS

Primary Endpoints:	The primary endpoint of this study is to investigate if pre-operative inter-papillary muscle separation (diastolic, systolic and diastolic-systolic) correlates with FMR severity at 12 months after surgery with UMA and UMA+PMA.
Secondary Endpoints:	
Survival
 
 
• All-cause mortality at discharge, 6 months and 1 year
 
 
Functional Status and Hospitalizations
 
 
• MACE MACE is defined as a non-weighted composite score comprised of the following: 
 
- Death
 
- Stroke
 
- Worsening heart failure (+1 NYHA class)
 
- CHF hospitalization
 
- Mitral valve re-intervention
 
 
 
• NYHA classification Functional status will be assessed by the NYHA classification scale. (Appendix 1)
 
• 6-minute walk test Functional status will also be measured by a 6-minute walk test, which assesses the distance walked (in feet) during the pre-specified time period. The test will be administered by a trained study coordinator. (Appendix 2)
 
• Readmission rates
 

Readmission rate will be calculated for any cause within the first 30 days and for all cause, cardiovascular and heart failure after 30 days following surgery. Classification of readmission as heart failure related requires at least 2 out of the following signs and symptoms of acute decompensated heart failure:

- Dyspnea felt related to HF
- Treatment with intravenous diuretic, vasodilator or inotropic therapy
- X ray evidence of pulmonary edema or pulmonary vascular congestion
- Rales on physical exam
- PCWP or LVEDP > 18mm Hg

All readmissions will be classified by the investigator and adjudicated by the event adjudication committee.

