### **Physiologic**

- **Echocardiographic parameters**

*Presence and severity of mitral regurgitation* will be assessed by measuring the effective regurgitant orifice area (EROA) by both the proximal isovelocity surface area and the quantitative flow methods. If it is not possible to assess MR using these techniques, MR will be assessed by tracing the jet area and normalizing by the left atrial area.

*Mitral valve apparatus* and quantification of valve area will be assessed by evaluating annular shape and motion, tethering angle and tenting area, papillary muscle position and separation, and calculation of mean trans-mitral stenotic gradient by mitral inflow continuous wave Doppler.

*LV size, geometry and function* will be assessed by the following measures: LV dimensions, ejection fraction (biplane Simpson's rule), LV end-systolic volume index using the biplane volumetric method, LV mass, LV sphericity, radial strain, and twist.

*RV size and function* will be assessed by the following measures: tricuspid annular plane systolic excursion (TAPSE), peak systolic velocity, diastolic E and A velocity (by tissue doppler), and fractional area change.

*Left atrial dimension and volume* will be assessed.

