## 11.0 ANALYSIS PLAN

**General design issues:** This is an observational, prospective, non-randomized, single center, multiple phase study. Enrolled patients will have clinically significant FMR with either ischemic or non-ischemic cardiomyopathies. 50 patients are recruited to phase 1 (all 50 receiving undersizing mitral annuloplasty), and 90 patients to phase 2 (75 receiving undersizing mitral annuloplasty and 15 receiving undersizing mitral annuloplasty and papillary muscle approximation). In patients

receiving undersizing mitral annuloplasty, the same rigid annuloplasty ring will be used as consistently as possible, and up to two sizes of downsizing will be performed as consistently as possible. In some patients recruited to the study, the surgeon may decide to switch to mitral valve replacement, or may perform a repair and deem it to be a failure and then switch to mitral valve replacement. In either case, the patient will continue to be part of the study, but with follow-up performed only at 12 months.

**Sample size estimation and statistical analysis plan:** The primary objective of this study is to determine the correlation between pre-operative inter-papillary muscle separation and the 6 month and 12 month post-operative FMR grade after undersizing mitral annuloplasty. Pre-operative inter-papillary muscle separation will be measured and is a continuous variable, while the recurrence of FMR will be deemed binary (1: if MR greater than or equal to 2+ severity observed at 12 months; 0: if MR less than or equal to 2+ severity observed at 12 months). An ROC curve analysis will be used to determine the inflection point of inter-papillary muscle separation at which FMR will recur at 12 months after annuloplasty. Sample sizes are based on previously published data, and on ensuring the ability to detect with high probability, a clinically meaningful presumed benefit for patients undergoing mitral valve repair.

Recruitment to the papillary muscle approximation arm is not based on power analysis as it is only a pilot study.

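### The primary question is whether IPMS correlates with 12-month FMR severity, but the only named analysis is an ROC curve on binary recurrence, so severity itself has no named analysis

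*Combined protocol and SAP*

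**What the plan says.** - **Primary endpoint (Sections 1.0 and 9.0).** The question is whether pre-operative IPMS, taken as diastolic, systolic and the difference between them, "correlates with FMR severity at 12 months after surgery with UMA and UMA+PMA".
- **Objective (Section 2.0).** The primary objective is prediction of 12-month FMR severity after undersizing mitral annuloplasty (UMA). It then adds a second aim: "whether a cut-off value of pre-operative inter-papillary muscle separation can be established to predict patients who might have failure of UMA". Section 3.0 repeats the cut-off aim.
- **Objective as restated (Section 11.0).** The study is to "determine the correlation between pre-operative inter-papillary muscle separation and the 6 month and 12 month post-operative FMR grade". No coefficient, model or test is attached to this.
- **Outcome as analysed (Section 11.0).** IPMS stays continuous, "while the recurrence of FMR will be deemed binary", with the coding "1: if MR greater than or equal to 2+ severity observed at 12 months; 0: if MR less than or equal to 2+ severity".
- **Method (Section 11.0).** "An ROC curve analysis will be used to determine the inflection point of inter-papillary muscle separation". No other method is named, and the 6-month grade has no analysis.
- **Severity data (Section 9.0, echocardiographic parameters).** Mitral regurgitation "will be assessed by measuring the effective regurgitant orifice area (EROA) by both the proximal isovelocity surface area and the quantitative flow methods", with a jet-area ratio where that is not possible. The Section 1.0 endpoint list has effective regurgitant orifice and regurgitant fraction at discharge, 30 days, 6 months and 12 months.

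**The concern.** The stated question is about degree: does regurgitation at 12 months get worse as IPMS gets larger? The named analysis asks only whether a patient crosses one threshold. It treats every grade on the same side of that threshold as equal, so a patient just over the line counts the same as one with severe regurgitation.

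Two things are at stake. First, the severity question has no pre-specified answer. The scale, the coefficient and the choice among three IPMS measures could all be settled after the data are seen. Second, splitting a graded or continuous outcome in two discards information. Section 11.0 gives no alpha, power, effect size or dropout, so nothing shows that 125 patients can absorb that loss.

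**Working it through.** **The plan's own figure.** The UMA group is 125. It cannot be reproduced, because no alpha, power, effect size, standard deviation or dropout is stated. Only the addition checks: 50 + 75 = 125 UMA patients, and 125 + 15 = 140 in total.

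**Inputs from the documents.** UMA group of 125 (Sections 1.0 and 7.2). Recurrence at 12 months of 32.6% (Section 1.0, Precis) or about 36% (Section 3.0).

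**Inputs assumed.** Severity is a normal latent variable. Correlation r with IPMS is small. Tests are two-sided at 5%, with no dropout. The number of grades and their distribution are not in the documents. The binary outcome is taken as properly defined, although the printed coding puts exactly 2+ in both classes.

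**Step 1. Binary against continuous severity.** For small r, the information kept by a split at recurrence rate p is E = φ(z)² / [p(1−p)], where z is the upper-p normal quantile and φ the normal density.

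- p = 0.326: φ(0.451) = 0.3604, so E = 0.1299 / 0.2197 = 0.591. The loss is 40.9%, and 125 × 0.591 ≈ 74 patients.
- p = 0.36: φ(0.358) = 0.3741, so E = 0.1400 / 0.2304 = 0.607. The loss is 39.3%, and 125 × 0.607 ≈ 76 patients.
- The smallest possible loss, at p = 0.5, is 36.3%. At p = 0.20 it is 51%, and at p = 0.10 it is 66%.

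**Step 2. Binary against grade, the scale Section 11.0 names.** For grades with proportions p_k, the information kept is E = Σ (φ(c_{k−1}) − φ(c_k))² / p_k, where the c_k are the normal cut-points. Take five grades cut at the 35th, 67.4th, 85th and 95th percentiles (assumed). The densities at the cuts are 0.3704, 0.3604, 0.2332 and 0.1031. The five terms are 0.3920 + 0.0003 + 0.0919 + 0.1691 + 0.2127 = 0.866. Binary relative to grade is 0.591 / 0.866 = 0.682, a loss of about 32%.

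Other assumed distributions at p = 0.326:

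| Grades | Proportions | E (grade) | Loss from splitting |
|---|---|---|---|
| 5 | 0.30, 0.374, 0.20, 0.10, 0.026 | 0.876 | 32.5% |
| 4 | 0.35, 0.324, 0.25, 0.076 | 0.850 | 30.5% |
| 4 | 0.40, 0.274, 0.20, 0.126 | 0.833 | 29.1% |
| 3 | 0.30, 0.374, 0.326 | 0.802 | 26.3% |

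At p = 0.36 the graded losses are slightly smaller. Three grades of 0.30, 0.34 and 0.36 give E = 0.794, so the loss is 1 − 0.607/0.794 ≈ 24%. A fair summary is roughly 25–33%.

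**Step 3. Power by simulation.** n = 125, bivariate normal, five-level cuts as in Step 2, binary split at the 67.4th percentile.

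| True r | Continuous (Spearman) | Five-level grade (Spearman) | Binary (Mann–Whitney) |
|---|---|---|---|
| 0.25 | 77% | 73% | 57% |
| 0.30 | 90% | 87% | 72–73% |

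A Pearson test on exactly normal severity gives 81% and 93%. The rank tests are the fairer comparison for grades. Spearman on the grade stands in for the ordinal regression proposed below, whose own power was not simulated.

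**The case against.** The strongest reply is that a binary outcome is not a mistake here. The hypothesis in Section 1.0 is about failure of the repair and recurrence, and Section 2.0 asks for a cut-off that predicts failure. An ROC curve on binary recurrence is the natural analysis for that, and the area under it measures association between IPMS and recurrence. This stands. A reader might infer that dichotomising is an error, or that the primary endpoint has no analysis at all. The documents support neither: the cut-off part is served, and what is missing is an analysis of severity beside it.

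A reader might also take the loss to be about 40% outright. That figure applies to a continuous, normally distributed severity. Section 11.0 names FMR grade, against which the loss is roughly 25–33%.

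The continuous ideal is optimistic in other ways too. Patients with no residual regurgitation would tie at zero, and Section 9.0 allows a jet-area fallback. If the lowest 35% are tied, simulated Spearman power at r = 0.25 falls from 77% to 74%. Both recurrence figures are cited to a trial whose title refers to severe ischemic regurgitation, while this study enrols moderate or greater regurgitation of ischemic or non-ischemic origin. The rate here may therefore differ. These points change the size of the loss, not the absence of a named severity analysis.

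**Conclusion.** The point holds in a limited form. The primary question is stated on the severity or grade scale, and the one analysis named works on a cruder scale. That mismatch is plain in the text and depends on no calculation.

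Under the assumptions in the working, five-level grade analysis gains about 73 − 57 = 16 percentage points of power at r = 0.25 and about 14 at r = 0.30. None of these figures is in the documents, and they move with the recurrence rate, the grade distribution and dropout. They do not show that the study is underpowered, because no target effect or power is stated to judge it against.

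**What to change.** In Section 11.0:

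1. Name as the primary analysis a proportional-odds regression of 12-month MR grade on pre-operative IPMS in the UMA group. State the grade levels.
2. Pre-name one primary IPMS measure: phase (diastolic, systolic or difference) and location (tip, mid-body or base, all listed in Section 9.0). Report the others as secondary.
3. Add Spearman correlation of IPMS with EROA as support, in patients where EROA is measurable.
4. Keep the binary outcome and ROC curve solely to derive the cut-off, and settle which class exactly 2+ belongs to.
5. Either name an analysis for the 6-month grade or drop it from the stated objective.

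The cost is a change of wording, one more model and a proportional-odds assumption to check. No new data or visits are needed.

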## 1.0 PROTOCOL SUMMARY

Title	Improving mitral repair for functional mitral regurgitation (IMPROVE-FMR)
Precis	
Functional mitral regurgitation (FMR) can have an adverse impact on the cardiomyopathic left ventricle, by imposing a chronic low-pressure volume overload. Unrepaired FMR increases the risk of congestive heart failure and death. Undersizing mitral annuloplasty (UMA) is the current gold standard for repair of FMR, but its outcomes are poor with 32.6% of patients presenting with clinically significant recurrent FMR at 1 year after the repair, which increases to 58.8% of the patients at 2 years after annuloplasty. Currently, we do not understand why some patients have failure of annuloplasty, while others do not. Lack of mechanistic insights has inhibited an evidence driven approach in optimizing the repairs adequately – resulting in plethora of new sub-valvular techniques, but very few with appropriate scientific justification to be tested in randomized trials.
 
Our team recently performed a retrospective cardiac MRI study in FMR patients and identified that inter-papillary muscle separation (IPMS) is a strong determinant of FMR severity prior to undergoing any repair. Using image-derived computational biomechanical modeling, we reported that when IPMS is elevated, marginal chordal forces restrict parallelization of the leaflet edges and cause higher FMR. We built upon this observation, and performed an ex vivo bench study to demonstrate that IPMS is a strong determinant of repair success as well. In this study, we demonstrated that the MR volume after repair is directly correlated to the pre-operative IPMS. We recently advanced this study further into a chronic swine model, and demonstrated that swine undergoing papillary muscle approximation (PMA) alone or concomitantly with undersizing mitral annuloplasty (UMA), have better valvular function at 3 months after surgery, compared to animals that receive UMA alone. Their valvular kinematics were superior, and so was their ventricular function.
 
In this observational, prospective, non-randomized study in humans with FMR, we seek to investigate the following:
 

• Question 1: Does pre-operative IPMS correlate with the severity of FMR after UMA at 30 days, 6 months and 12 months. We will study this primary objective by conducting pre-operative MRI and echo in patients receiving UMA, and follow them to one year. Secondly, we will use these images from each patient as input to a computational biomechanical model, which will help demonstrate the chordal forces and stresses before repair, after repair and at the follow-up time points. We will recruit a total of 125 patients to this phase of the study.

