### **3.0 BACKGROUND**

Functional mitral regurgitation (FMR) is a frequently diagnosed mitral valve lesion in patients surviving cardiomyopathies of ischemic and non-ischemic origins. Volume overload from FMR increases the risk of congestive heart failure and death. Pharmacological management of these patients has been shown to be ineffective, and thus timely repair of FMR is considered to benefit the patient and preserve their cardiac function.

Undersizing mitral annuloplasty (UMA) is the current standard of care to repair FMR, which involves placing a metallic ring onto the mitral annulus, to reduce its dimensions. This procedure can be performed using open heart surgical techniques or with transcatheter mitral valve techniques. Though UMA is considered effective, there is increasing evidence that FMR persists or recurs after the procedure. At 12 months, ~36% of the patients present with recurrence FMR, which increases to 58% at 24 months. The mechanisms driving failure of UMA are unknown, and a metric for pre-operative stratification of patients to benefit from UMA is necessary.

Our group recently reported that in patients presenting with FMR, inter-papillary muscle separation (IPMS) has a strong correlation with the pre-operative severity of the regurgitation. Using cardiac MRI imaging, we demonstrated that IPMS directly impacted the extent of leaflet tethering and mitral regurgitation, independent of the left ventricular size or volume. We used biomechanical modeling to demonstrate that elevated IPMS increases the forces in the marginal chordae, resulting in improper leaflet closure.

In a more recent study in a bench-top ex-vivo model, we demonstrated that IPMS can also have an impact on mitral valve closure after undersizing mitral annuloplasty (UMA). Specifically, we demonstrate that when the IPMS is elevated, UMA results in a highly unphysiological leaflet geometry that results in persistent FMR despite the repair. In a similar study in swine, we demonstrated that such an unphysiological leaflet configuration after UMA can be improved with papillary muscle approximation (PMA).

In this observational, prospective, non-randomized clinical study, we seek to test the hypothesis that elevated pre-operative inter-papillary muscle separation (IPMS) is a risk factor for recurrence

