of FMR after annuloplasty. Since high or low are subjective terms, we seek to recruit 125 patients undergoing undersizing mitral annuloplasty (UMA) at our institution and measure their inter-papillary muscle separation before and after the procedure, and study their impact on 12 month outcomes of the repair. We will perform statistical analysis to determine a cut-off value for IPMS that can stratify patients at risk for UMA failure.

Using the patient specific imaging that we obtain from the 125 patients, we will perform comprehensive biomechanical computational modeling to demonstrate and validate that patients below the cut-off value of IPMS have better mitral valve force distribution, vs. those above the cut-off value of IPMS having poor mitral valve force distribution. This data will help validate the cut-off value as a viable technique to stratify patients for UMA.

In the final step of this study, we will demonstrate that those patients with higher IPMS and at risk of UMA failure, may benefit from a concomitant papillary muscle approximation technique. We will recruit 15 patients to a pilot study, in whom IPMS is above the cut off value, and perform papillary muscle approximation (PMS) along with undersizing mitral annuloplasty (UMA). We will investigate the effect of this combination approach on the outcomes at 6 months and 12 months.

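### The 12-month recurrence codes overlap at exactly 2+ MR, so these patients have no unique outcome in the ROC analysis that sets the IPMS cut-off

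*Combined protocol and SAP*

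**What the plan says.** Section 11.0, under sample size estimation and statistical analysis plan, treats pre-operative IPMS as continuous and recurrence as binary, coded "1: if MR greater than or equal to 2+ severity observed at 12 months; 0: if MR less than or equal to 2+ severity". It then states: "An ROC curve analysis will be used to determine the inflection point of inter-papillary muscle separation at which FMR will recur at 12 months".

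The resulting cut-off matters elsewhere in the protocol:

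- Section 2.0 includes in the primary objective "whether a cut-off value of pre-operative inter-papillary muscle separation can be established to predict patients who might have failure of UMA".
- Section 3.0 describes the pilot group this way: "We will recruit 15 patients to a pilot study, in whom IPMS is above the cut off value". It also plans to compare modelled valve forces in patients below and above the cut-off.

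The endpoint labelled primary in Sections 1.0 and 9.0 is worded differently. It asks whether IPMS "correlates with FMR severity at 12 months after surgery with UMA and UMA+PMA", and gives no recurrence threshold.

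For echocardiographic severity, Section 9.0 specifies effective regurgitant orifice area. Where that is not possible, "MR will be assessed by tracing the jet area and normalizing by the left atrial area". Regurgitant fraction appears in the Section 1.0 endpoint list, and Section 9.0 also gives an MRI measure of regurgitation.

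**The concern.** A binary outcome has to place every patient in exactly one class. Here the two classes share the grade 2+, which is the boundary between success and failure. The recurrence rate, the AUC and the cut-off can all depend on which class those patients join.

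As written, the outcome cannot be programmed without a decision that the plan does not contain. If that decision is made after outcomes are known, the analyst can see which coding gives the better AUC or the more convenient cut-off. The chosen cut-off would then be used to label patients as at risk of annuloplasty failure, to form the groups in the modelling comparison and, according to Section 3.0, to define the pilot patients.

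**Working it through.** **Step 1. The overlap.** Code 1 covers MR ≥2+ and code 0 covers MR ≤2+. Their intersection is MR = 2+. Every other grade receives one code. Both limits are written in words, so a symbol lost in the PDF does not explain it.

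**Step 2. Does another section break the tie?**

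| Place | Wording on the outcome | Resolves 2+? |
|---|---|---|
| Sections 1.0 and 9.0, primary endpoint | FMR severity, no threshold | No |
| Section 2.0 | failure of annuloplasty, undefined | No |
| Section 1.0, Precis | "32.6% of patients presenting with clinically significant recurrent FMR at 1 year after the repair" | No grade given |
| Section 3.0 | "At 12 months, ~36% of the patients present with recurrence FMR" | No grade given |
| Sections 1.0 and 7.2, inclusion criteria | moderate or greater MR | Entry criterion only |
| Section 9.0, echo and MRI | orifice area, jet-area ratio, MRI regurgitation | No mapping to 2+ |

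Sections 7.2 and 8.0 schedule a transthoracic echo at 12 months plus MRI and/or transesophageal echo. They do not say which examination supplies the grade.

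**Step 3. The plan's own figure.** The counts agree: 50 + 75 = 125 annuloplasty patients, and 125 + 15 = 140 in total. The 125 itself cannot be re-derived, because Section 11.0 gives no alpha, power, effect size, target AUC, precision or dropout.

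**Step 4. Illustration of size.** Inputs from the document: N = 125 and a quoted 12-month recurrence of 32.6% (Section 1.0) or about 36% (Section 3.0). Assumptions: a share q of 5% to 25% at exactly 2+, an AUC of 0.70, and all 125 patients evaluable. The grade behind the quoted rates is not given, so both readings are shown.

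- Patients carrying both codes: 125q = 6.25 to 31.25.
- Reading (a): the quoted rate is for ≥2+ and 2+ is coded 0. Events = 125(0.326 − q).
- Reading (b): the quoted rate is for >2+ and 2+ is coded 1. Events = 125(0.326 + q).

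The Hanley-McNeil standard error, with n1 events and n0 = 125 − n1, is

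SE² = [A(1−A) + (n1−1)(Q1−A²) + (n0−1)(Q2−A²)] / (n1·n0), where Q1 = A/(2−A) and Q2 = 2A²/(1+A).

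At A = 0.70, Q1 = 0.5385 and Q2 = 0.5765. The base case has 125 × 0.326 = 40.75, or about 41 events, and 84 non-events. SE² = [0.21 + 40(0.0485) + 83(0.0865)] / 3444 = 0.00271, so SE = 0.052 and 1.96 × SE = 0.102.

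| q | Patients at 2+ | (a) events (rate) | Half-width | (b) events (rate) | Half-width |
|---|---|---|---|---|---|
| 5% | 6 | 35 (27.6%) | 0.108 | 47 (37.6%) | 0.098 |
| 10% | 13 | 28 (22.6%) | 0.118 | 53 (42.6%) | 0.094 |
| 15% | 19 | 22 (17.6%) | 0.131 | 60 (47.6%) | 0.092 |
| 20% | 25 | 16 (12.6%) | 0.150 | 66 (52.6%) | 0.091 |
| 25% | 31 | 10 (7.6%) | 0.187 | 72 (57.6%) | 0.091 |

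Counts are rounded to whole patients. With 36% instead, the base is 45 events and a half-width of 0.099. Reading (a) gives 39 down to 14 events (0.104 to 0.160) and reading (b) gives 51 up to 76 (0.095 to 0.091).

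**Step 5. Movement of the cut-off.** The document has no data from which to estimate this. A bivariate-normal simulation used an assumed IPMS–MR correlation of 0.3 or 0.5, 10% or 20% at exactly 2+, and 32.6% as the ≥2+ rate. The cut-off was taken as the Youden point.

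| Correlation | q | Cut-off, ≥2+ rule (SD) | Cut-off, >2+ rule (SD) | Shift (SD) |
|---|---|---|---|---|
| 0.3 | 10% | 0.05 | 0.15 | 0.10 |
| 0.3 | 20% | 0.05 | 0.20 | 0.15 |
| 0.5 | 10% | 0.13 | 0.18 | 0.05 |
| 0.5 | 20% | 0.13 | 0.28 | 0.15 |

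**The case against.** The strongest reply is that this is a one-word drafting slip with limited consequences. The labelled primary endpoint is a correlation with severity and does not use the binary code. The simulated shift in the cut-off is small. The 5 to 25 point change in the recurrence rate only restates the assumed share at 2+. The worst row of the table needs 31.25 of 40.75 recurrences, about 77%, to sit at exactly 2+. Under reading (b), precision improves slightly.

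The pilot link is also looser than Section 3.0 suggests. Section 11.0 recruits the 15 pilot patients in phase 2 alongside 75 annuloplasty patients, and Section 7.2 says only that assignment is not randomized. The cut-off used for selection may come from the 50 phase 1 patients, in which case the figures for 125 would not describe it. Finally, mapping orifice area or jet area to a grade is a separate matter that would remain after the codes are corrected.

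All of these points about size and scope stand. The argument that it is merely a slip does not. A slip can be read through when it has one evident correction; here there are two (≥2+ versus <2+, or >2+ versus ≤2+), and the document favours neither.

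**Conclusion.** The concern holds. As written, the outcome behind the ROC analysis is contradictory at exactly 2+, and no other section resolves it. The defect reaches the 12-month recurrence rate, the AUC and the cut-off in the primary objective, together with whatever uses that cut-off later. It does not reach the correlation of IPMS with graded severity.

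The size is unknown. Under the stated assumptions about 6 to 31 of 125 patients are affected, and AUC precision may worsen materially or improve slightly. The cut-off moved by only 0.05 to 0.15 SD in the one simulation available. The correction is nonetheless necessary, because the outcome cannot be coded uniquely and the choice should not be made with results in hand.

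**What to change.** Before any 12-month outcome is analysed, amend Section 11.0 so that the codes are mutually exclusive: either ≥2+ versus <2+, or >2+ versus ≤2+. The sponsor should choose, consistently with the definition behind the recurrence rate it cites, and should state that definition.

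In the same amendment:

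- state how orifice area, regurgitant fraction and the jet-area fallback map to 2+;
- state which 12-month examination supplies the grade;
- report the other split as a sensitivity analysis, so that readers can see how far the AUC and the cut-off depend on the choice;
- say which data set provides the cut-off used to select pilot patients.

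The codes need one line of text and the grading rule a short definition. No new data or visits are required.

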Post-chest closure echo: Just prior to moving the patient out of the operating room, a repeat intra-operative standard-of-care echocardiogram will be performed to assess the valve function. After both procedures, the patients are revived from surgery and their post-operative care will follow established and standard of care protocols.

Follow-up time points and examinations:

*Discharge:* Following examinations will be performed before discharge:

- Transthoracic echocardiography

- Blood draw

*30-day (+/- 7 days):* Following examinations will be performed at 30-days :

- Blood draw
- Transthoracic echocardiography

*6 months post-surgery (+/- 30 days):* Following examinations will be performed at discharge at 6 months post-surgery

- Transthoracic echocardiography
- Blood draw
- Quality of life questionnaire
- HF questionnaire
- 6 minute walk test

*12 months post-surgery (+/- 90 days):* Following examinations will be performed at discharge at 6 months post-surgery

- Transthoracic echocardiography
- Cardiac MRI with contrast or transesophageal echo (whichever is possible)
- Blood draw
- QoL questionnaire
- Heart failure questionnaire
- 6MWT

Computational biomechanical modeling: Echocardiographic images, immediately after acquisition will be transferred to the core database established by the PI's laboratory. These images obtained from the patients at the different timepoints will be used for computational biomechanical modeling. The 3D echocardiographic images will be segmented and a mathematical mesh will be developed. Idealized material properties will be assigned to the mesh geometry, and the strain and stress distribution on the leaflets will be quantified under different loading conditions.

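### The ROC outcome is named recurrence but counts all MR present at 12 months, so MR that the repair never abolished is reported as recurrence

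*Combined protocol and SAP*

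**What the plan says.** Section 11.0 (sample size and statistical analysis) states that "the recurrence of FMR will be deemed binary". Code 1 is "1: if MR greater than or equal to 2+ severity observed at 12 months" and code 0 is "0: if MR less than or equal to 2+ severity observed at 12 months". The use of the variable, with annuloplasty as the starting point, is then given: "An ROC curve analysis will be used to determine the inflection point of inter-papillary muscle separation at which FMR will recur at 12 months after". Neither this section nor any other makes the code depend on the MR grade after the repair.

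Section 3.0 keeps the two routes to late MR apart: "there is increasing evidence that FMR persists or recurs after the procedure". It also reports the group's bench finding that, when IPMS is elevated, "UMA results in a highly unphysiological leaflet geometry that results in persistent FMR despite the repair".

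Early post-operative MR is measured. Section 7.2 says of chest closure that "a repeat intra-operative standard-of-care echocardiogram will be performed to assess the valve function". Section 1.0 lists MR severity at chest closure (TEE) and at discharge and 30 days (TTE), and the Section 8.0 table marks all three echoes as standard of care.

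**The concern.** A patient discharged with MR above the threshold who still has it at 12 months receives the same code as one whose valve was competent after repair and leaked later. The variable is therefore the prevalence of MR at 12 months, although the plan gives it the name of an incident event.

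The difference matters for what the study can conclude. If IPMS marks only valves that the ring never made competent, the planned ROC would present it as a predictor of recurrence. If IPMS marks only later deterioration, residual cases would blur that relation and could shift the cut-off. The third objective in Section 2.0 is the mechanism of repair failure, and the planned ROC cannot tell these two patterns apart.

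**Working it through.** **Reading the definition.** The outcome is named recurrence, coded from one time point, and used to find the IPMS at which FMR will recur. No section adds a condition on MR at chest closure, discharge or 30 days. Applied exactly as written, the rule classes MR above 2+ that was never abolished as recurrence. At exactly 2+ the rule is undefined, because that grade satisfies both codes. This is a separate defect, but residual and recurrent cases cannot be separated until it is settled.

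**The plan's own figure.** The 125 UMA patients agree with the phase counts in Section 11.0 (50 + 75 = 125; 125 + 15 = 140). The number cannot be reproduced from a power calculation, because no alpha, power, target AUC or dropout is stated.

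**Expected cases.** Section 1.0 cites 32.6% at one year: 125 × 0.326 = 40.75, about 41 cases and 84 non-cases. Section 3.0 gives about 36%: 125 × 0.36 = 45 cases and 80 non-cases.

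**Effect of mixing (illustration).** When residual and recurrent cases are compared with the same non-cases, the pooled AUC is the case-weighted mean:

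pooled AUC = (1 − f) × AUC(recurrent) + f × AUC(residual),

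where f is the residual share of the cases. The documents give none of these three quantities, so all are assumed. For 8 residual cases of 41, with AUC 0.75 for recurrent and 0.50 for residual MR: 33/41 × 0.75 + 8/41 × 0.50 = 0.604 + 0.098 = 0.701.

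| Residual / recurrent cases | Recurrent 0.75, residual 0.50 | Recurrent 0.75, residual 0.85 | Recurrent 0.60, residual 0.85 |
|---|---|---|---|
| 4 / 37 | 0.726 | 0.760 | 0.624 |
| 8 / 33 | 0.701 | 0.770 | 0.649 |
| 12 / 29 | 0.677 | 0.779 | 0.673 |
| 16 / 25 | 0.652 | 0.789 | 0.698 |

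Pooling lowers the AUC for recurrence in the first scenario and raises it in the other two. The documents do not show which applies.

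**Precision of a split.** The Hanley-McNeil standard error with n1 cases, n0 = 84 non-cases and AUC A is

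SE² = [A(1 − A) + (n1 − 1)(Q1 − A²) + (n0 − 1)(Q2 − A²)] / (n1 × n0), with Q1 = A/(2 − A) and Q2 = 2A²/(1 + A).

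- Recurrent cases, A = 0.75: the 95% half-width (1.96 × SE) is 0.101, 0.106, 0.112 and 0.119 for 37, 33, 29 and 25 cases. With all 41 cases it is 0.097.
- Residual cases, A = 0.80: the half-width is about 0.22 with 6 cases and 0.16 with 12.

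The recurrent AUC loses little precision. The residual AUC is imprecise.

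**The case against.** The strongest reply is that the study's target is wider than recurrence. The hypothesis in Section 1.0 names failure of UMA as well as recurrence. Section 2.0 seeks a cut-off for patients in whom UMA may fail, and Section 3.0 describes the cut-off in the same terms. The primary endpoint is correlation with FMR severity at 12 months, with no condition on early success. For that target, MR at 12 months by either route is the right outcome. This stands, and it is why the pooled variable should remain primary.

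Second, the first objective in Section 1.0 already relates IPMS to FMR severity immediately after surgery and at 30 days, so an association confined to incomplete repair might show there. This stands in part. Those are separate correlations: they do not classify the 12-month cases that enter the ROC, and the method text in Section 11.0 does not mention them.

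Third, Section 11.0 lets the surgeon convert a repair judged to have failed to a replacement, which may remove some residual cases from code 1. That is fair, but no MR limit is given for conversion, so residual MR is not excluded. How converted patients enter the ROC is not stated.

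A reader might go further and infer that mixing invalidates the primary ROC, or that it biases the AUC in a known direction. The documents support neither. The AUC and cut-off are valid for 12-month failure, and the direction depends on quantities the documents do not give. Nor can residual MR be assumed unrelated to IPMS: the bench finding in Section 3.0 links the two.

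**Conclusion.** The point holds as one of naming and interpretation, with a useful secondary analysis missing. Following Section 11.0 exactly would report as recurrence some MR that was there from the start, so the planned ROC can support a statement about UMA failure at 12 months but not one about recurrence.

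The size is unknown. The illustrated shifts in AUC, from about 0.10 down (0.75 to 0.652) to about 0.10 up (0.60 to 0.698), rest on an assumed residual share of roughly 10% to 40% of cases, on assumed AUCs, and on 41 cases among 125 patients with complete 12-month data. They show that the effect could matter and could go either way; they do not estimate it.

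**What to change.** 1. Resolve the overlap of codes 0 and 1 so that a grade of exactly 2+ belongs to one code only.
2. Keep the pooled 12-month outcome for the primary ROC and name it *UMA failure at 12 months*.
3. Pre-specify a secondary analysis that splits the cases into residual (at or above the threshold by discharge and at 12 months) and recurrent (below it at discharge, at or above it at 12 months). Report the IPMS AUC with a 95% CI for each against the same non-failures, and use the word recurrence only for the second type.
4. Classify early status with the discharge TTE, the same modality as the 12-month TTE, and use the chest-closure TEE as supporting evidence. Section 11.0 does not name the modality for the 12-month grade, so state it.
5. Report patients without an early echo as unclassified. This may arise in Registry 3, the chart review back to 2004. State how patients converted to replacement are handled in the analysis.

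The cost is SAP wording and one extra analysis of echoes already scheduled, with no added visits. The primary AUC and cut-off do not change because of the renaming or the split; settling the code at 2+ is needed in any case. The downside is that the residual group is likely to be small, so its AUC should be labelled exploratory.
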